7.2 Study Intervention Adherence

All staff and clinicians will be trained in the protocol by an experienced staff member. To ensure provider skill acquisition we will use role playing. Fidelity to the treatment protocols, content, information, and delivery will be assessed using observation checklists. To minimize provider and intervention 'drift', we will meet every-other-week to discuss intervention strategies and problem solve challenges including adherence with the use of vouchers and grocery boxes. We will have weekly team meetings to discuss participant progress and protocol adherence.

Attendance of intervention sessions will be used to assess adherence to the BWL treatment. Redemption rates of vouchers will be assessed using receipts collected every 2 weeks. Data will be extracted on date of purchase, grocery items purchased and grocery items' price. Each food item will be coded into broader categories of food (e.g., fruits, vegetables) based on the USDA food guidelines. Consumption of items from food boxes will be reviewed with a standardized checklist. Food resource connection and enrollment will be assessed with a questionnaire at each outcome assessment.

7.3 Concomitant Therapy

For this protocol, a prescription medication is defined as a medication that can be prescribed only by a properly authorized/licensed clinician. Medications to be reported in the Case Report Form (CRF) are concomitant prescription medications, over-the-counter medications and supplements. Concomitant medications will be assessed at baseline, weeks 12 and 24.

7.3.1 Rescue Medicine

The study site will not supply rescue medications. During this study, participants will be asked to refrain from joining another structured weight loss program, starting a weight loss medication, or receiving bariatric surgery. If participants do begin a weight loss medication or have bariatric surgery, they will be allowed to continue in the study treatment and assessments, and it will be documented in participant forms and analyzed using sensitivity analyses.

8 STUDY INTERVENTION DISCONTINUATION AND PARTICIPANT DISCONTINUATION/WITHDRAWAL

8.1 Discontinuation of Study Intervention

Discontinuation from the study intervention does not mean discontinuation from the study. If participants are willing, we will ask them to complete study assessments as indicated by the study protocol. If a clinically significant finding is identified (including, but not limited to changes from baseline) after enrollment, the investigator or qualified designee will determine if any change in participant management is needed. Any new clinically relevant finding will be reported as an adverse event (AE).

The data to be collected at the time of study intervention discontinuation will include the following:

- Follow-up assessment measures
- Follow-up questionnaires
- Reason for discontinuation

8.2 Participant Discontinuation/Withdrawal from the Study

Participants are free to withdraw from participation in the study at any time upon request.

An investigator may discontinue or withdraw a participant from the study for the following reasons:

- Pregnancy
- If any clinical adverse event (AE) or other condition or situation occurs such that continued participation in the study would not be in the best interest of the participant

The reason for participant discontinuation or withdrawal from the study will be recorded on the Case Report Form (CRF). Participants who sign the informed consent form and are randomized but do not attend the randomization visit may be replaced. Participants who sign the informed consent form and are randomized and receive the study intervention (i.e., attend the first BWL visit after the randomization visit), and subsequently withdraw, or are withdrawn or discontinued from the study, will not be replaced.

For participants that may discontinue or withdraw early, we will capture the rationale during the final visit.

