5.4 Strategies for Recruitment and Retention

Participants will be recruited utilizing a multimodal strategy. Participants will be recruited using advertisements and flyers in print, newspaper, radio, and social media outlets. We will also recruit participants in collaboration with community partners, referrals from primary care practices at the University of Pennsylvania Health Care System, and food pantries. We will be recruiting from the university-based website, iConnect, which allows access to their volunteer registry data of potential participants. We will use study condition terms such as obesity. Recruitment may also use Penn media services (e.g., communications) and social media (e.g., Facebook, Twitter). Social media recruitment will be limited to one-way advertisements.

Retention during follow-up will be promoted with strategies such as: providing reimbursement for travel; conducting assessment visits at convenient times for participants (e.g., early morning, weekends); emphasizing the clinical and research obligations of the study; and addressing potential participant disappointment with being assigned to a particular study condition.

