5.5 Measures to Minimize Bias: Randomization and Blinding

A permuted block randomization method will be used to assign participants to one of the three intervention groups in a 1:1:1 ratio. Once eligibility is confirmed, intervention assignment will be made by a pre-programmed randomization scheme. Block sizes will be varied to minimize potential bias, and randomization will be stratified by baseline SNAP/WIC receipt (vs no receipt). All participants who are randomized will be entered into the study database and analyzed according to Consolidated Standards of Reporting Trials guidelines for multi-arm parallel-group randomized trials.¹¹¹ This is an open-labelled randomized trial.

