- Review of medications
- Waist circumference
- Blood pressure and heart rate
- Urine pregnancy test (if unsure about pregnancy status)
- Questionnaires
 - Demographic data
 - Short Form-36 (SF-36)
 - Impact of Weight on Quality of Life-Lite (IWQOL-Lite)
 - US Adult Food Security Survey, 10 item
 - Eating Disorder Examination Questionnaire (EDE-Q)
 - Patient Health Questionnaire 8 (PHQ-8)
 - Eating Behavior Inventory (EBI)
 - Eating Self-Efficacy Survey
 - Perceived Nutrition Environment
 - Neighborhood Environment Walkability Scale
- 24-hour dietary recall interview
- Skin carotenoid assessment
- A second 24-hour dietary recall will be scheduled within 7 days and will need to be completed before the participant is randomized.

Randomization visit. The randomization visit will occur within two weeks of the second dietary recall (scheduled within 7 days after the baseline assessment visit). For randomized participants, the first BWL visit will also occur at this visit.

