10.3 Populations for Analyses

Populations for analyses will include:

- Intention-to-Treat (ITT) Analysis Dataset (i.e., all randomized participants)
- Per-Protocol Analysis Dataset: subset of the participants in the full analysis (ITT) set who complied with the protocol sufficiently to ensure that these data would be likely to represent the effects of study intervention according to the underlying scientific model (e.g., participants attended at least 80% of study intervention visits; participants reported consuming at least 50% of food purchased with food vouchers (BWL+VOUCHER) or 50% of food they received from food boxes (BWL+HOME))

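### Randomized people who miss the randomization visit may be replaced at staff discretion, and the plan does not reconcile this with the all-randomized ITT set or the target of 105.

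*Combined protocol and SAP*

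**What the plan says.** **Replacement.** Section 8.2 of the combined protocol and SAP: "Participants who sign the informed consent form and are randomized but do not attend the randomization visit may be replaced". The wording is permissive and gives no criteria. The next sentence rules out replacement of those who have received the intervention, which it explains as those who "attend the first BWL visit after the randomization visit".

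**Assignment.** Section 5.5: "Once eligibility is confirmed, intervention assignment will be made by a pre-programmed randomization scheme". This ties assignment to eligibility, not to attendance at a visit. The same section says "This is an open-labelled randomized trial".

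**Analysis set.** Section 10.3 lists the "Intention-to-Treat (ITT) Analysis Dataset (i.e., all randomized participants". Section 5.5 adds: "All participants who are randomized will be entered into the study database and analyzed according to Consolidated Standards of Reporting Trials guidelines". Section 10.4.2 makes the primary analysis an intention-to-treat linear mixed model of change from baseline to week 24.

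**Visit timing.** Section 6 allows the randomization visit up to two weeks after the second dietary recall, and says: "For randomized participants, the first BWL visit will also occur at this visit".

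**Target.** The Synopsis gives 105 participants, 35 per arm.

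**The concern.** A rule for replacing people who were randomized but did not attend only has work to do if assignment can exist before the visit. If so, someone can be assigned, fail to appear, and have another person recruited in their place. The plan leaves five things open:

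- whether the first person counts toward 105;
- whether that person is followed for weight;
- which assignment the newcomer receives;
- who decides on replacement;
- whether the person deciding knows the arm.

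At stake is the comparability of the arms in Aim 1. Suppose no-shows were more common in one arm, would have done worse than attenders, and supplied no outcome. The people contributing to that arm's estimate would then be a selected group. Section 10.2 gives effect-size estimation for a larger trial as the purpose of the study, so even a modest distortion would carry forward.

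A separate wording conflict blurs the rule's boundary. Section 6 places the first BWL visit at the randomization visit, while Section 8.2 speaks of it as coming afterwards. On the wording of Section 8.2, someone who attends the randomization visit but no later session is neither expressly replaceable nor expressly protected from replacement.

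**Working it through.** **Step 1: when does assignment happen?** There are two readings.

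- Assignment is made at the randomization visit. Then nobody can be randomized without attending, and the replacement sentence has no application.
- Assignment is made once eligibility is confirmed, as Section 5.5 says. Then the sentence applies, and up to two weeks may separate the second recall from the visit.

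On either reading, Sections 5.5, 6 and 8.2 need to be brought into line.

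**Step 2: does replacement remove anyone from ITT?** No section says so. Sections 5.5 and 10.3, read literally, keep every randomized person. On that reading the ITT denominator is 105 plus the number replaced. The planned figure is 3 × 35 = 105. If every no-show were replaced until 105 attended, the number randomized would be 105 / (1 − r), rounded up, where r is an assumed no-show rate:

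| Assumed r | Number randomized |
|---|---|
| 2% | 108 |
| 5% | 111 |
| 10% | 117 |

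**Step 3: does ITT membership protect the comparison?** The outcome in Section 10.4.2 is change from baseline. A person with no week 12 or week 24 weight has no change value and contributes nothing to the fit. Section 8.1 seeks assessments after the intervention is discontinued, but nothing says this reaches a replaced no-show. The missing-data sensitivity analyses in Section 10.4.1 are conditional on the missingness mechanism, and those in Section 10.4.2 add baseline covariates.

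**Step 4: how large could the effect be?** The documents give no no-show rates and no outcome gap, so all inputs here are assumptions. Let f be the share of an arm lost as no-shows, and g the gap in mean percent weight loss between attenders and no-shows, taken as equal across arms. The mean among attenders exceeds the all-randomized mean by f × g. The contrast (food arm minus BWL-Alone) is therefore reduced by

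(f in BWL-Alone − f in food arm) × g.

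Assume f of 5–15% in BWL-Alone, 0–5% in a food arm, and g of 3–5 points:

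- lowest: (0.05 − 0.05) × 3 = 0
- intermediate: (0.10 − 0.02) × 5 = 0.40 points
- highest: (0.15 − 0) × 5 = 0.75 points

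As a cross-check by head count, let k people beyond 35 be lost from one arm only, so f = k / (35 + k):

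| k | f | shift, gap 2 | shift, gap 5 |
|---|---|---|---|
| 1 | 2.8% | 0.06 | 0.14 |
| 2 | 5.4% | 0.11 | 0.27 |
| 4 | 10.3% | 0.21 | 0.51 |

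**Step 5: scale.** The standard error of a two-arm difference with 35 per arm is SD × √(2/35). That is 1.20 points for an assumed SD of 5 and 1.91 for an assumed SD of 8. Section 2.2 cites a food-provision trial in people without food insecurity with losses of 12.4% and 8.8%, a difference of 3.6 points. Against that, 0.40 is about 11% and 0.75 about 21%.

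**The case against.** The strongest reply is that Section 8.2 is only an enrolment rule. Replacing someone means recruiting another person, and Sections 5.5 and 10.3 still count the first as randomized and analysed. A reader might infer that the replacement rule contradicts the ITT definition, or that the plan gives two answers on who is analysed. The documents do not support that, and this part of the reply stands in full.

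A reader might also infer that arm-related exclusion is built in. That does not follow either. It needs the replaced people to drop out of the analysis in effect, and it needs the arm to be known to the participant before the missed visit or to whoever decides on replacement. The plan says when assignment is made, not when it is disclosed. If disclosure occurs only at the visit, a participant's absence cannot depend on arm. Section 5.4 does mention "addressing potential participant disappointment with being assigned to a particular study condition", but among strategies for retention during follow-up. It is not evidence that people learn their arm and then skip the randomization visit.

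A third point is that missing outcomes, not replacement, would cause any bias, and that deleting one sentence would not supply the missing weights. This is correct. It is why the remedy has to move the assignment to the visit and not merely remove the sentence.

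Finally, on Section 6's timing, anyone who attends the randomization visit has had the first BWL visit and so is not replaceable. That is a reasonable reading, but Section 8.2 words it differently.

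What remains after these replies is discretionary replacement without criteria, no stated timing of disclosure, no stated follow-up for replaced people, and two accounts of the first BWL visit.

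**Conclusion.** The point holds as a failure to reconcile sections, with a possible but undemonstrated route to bias. The plan permits replacement after randomization in an open-label trial. It does not say how replaced people are counted, followed or reported. Nominal ITT membership does not protect the comparison when a no-show has no follow-up weight.

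The likely size is small: 0 to 0.75 percentage points under the assumed rates and gaps, below the standard error of 1.20 to 1.91 under assumed SDs. The top value needs 15% against 0% no-shows. It also needs a 5-point gap, which equals the whole average loss of about 5% that Section 2.3.2 expects. If no-shows concentrate in BWL-Alone and would have lost less weight, the shift is toward the null, against the trial's own hypothesis. The opposite concentration would reverse the sign. The case for changing the text is that the change is nearly free, not that serious bias has been shown.

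**What to change.** - Generate and release the assignment only at the randomization visit, with the participant present and both baseline recalls done. Section 5.1 (completion of baseline assessments) and Section 6 (second recall before randomization) already require the baseline part. A no-show then meets the Section 5.3 definition of a screen failure, having consented but not been randomized. Recruiting someone else no longer touches the randomized set.
- Delete the replacement sentence in Section 8.2.
- For anyone already randomized and replaced: keep them in the ITT set, seek their week 12 and week 24 assessments where they are willing, and report them by arm in the participant flow. Any replacement takes the next assignment in the schedule, not the vacated one, because reusing a vacated slot would make that allocation known in advance.
- Reconcile Sections 6 and 8.2 on whether the first BWL visit occurs at the randomization visit or after it.

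The cost is a short wording amendment and a change in the timing of one database step. No visits or staff are added.

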8.3 Lost To Follow-Up

A participant will be considered lost to follow-up if he or she fails to return for the week 24 assessment (+4 weeks) and is unable to be contacted by the study site staff.

The following actions must be taken if a participant fails to return to the clinic for a required study assessment visit:

- The site will attempt to contact the participant and reschedule the missed visit and counsel the participant on the importance of maintaining the assigned visit schedule and ascertain if the participant wishes to and/or should continue in the study.
- Before a participant is deemed lost to follow-up, the investigator or designee will make every effort to regain contact with the participant (where possible, 3 telephone calls and, if necessary, a certified letter to the participant's last known mailing address or local equivalent methods). These contact attempts will be documented in the participant's medical record or study file.

Should the participant continue to be unreachable for their week 24 assessment, he or she will be considered to have withdrawn from the study with the primary reason of lost to follow-up.

9 STUDY ASSESSMENTS

9.1 Efficacy Assessments

Research staff will conduct assessments at our Center at weeks 0 (baseline), 12 and 24. All measures will be administered at all timepoints. Assessment staff will receive training in adherence to the data collection protocol. Questionnaires will be completed on REDCap, a secure, web-based program (if requested, participants can completed questionnaires on paper). To provide compensation for time and travel, participants will be paid \$40 per assessment. We will provide participants with ClinCards, which are similar to debit cards, that we have used for other studies. This form of payment allows us to load money remotely, enabling us to compensate participants soon after they complete study tasks.

Demographic and neighborhood data. Standard questionnaires will be administered to collect data on demographics at week 0 including age, biological sex, gender, race/ethnicity, income, street address, zip code, receipt of SNAP and/or WIC, household size, disabilities, marital status, and highest education level. We will recollect these data at weeks 12 and 24 to account for changes in status. We will also collect descriptive data at each timepoint on neighborhood food and physical activity environment including the Perceived Nutrition Environment Measures Survey¹³³ and Neighborhood Environment Walkability scale.¹³⁴

Weight and height. Weight will be measured in light clothes and no shoes, after an 8-hour fast, using a standardized scale calibrated monthly and accurate to 0.1 kg. Weight will be measured in duplicate. Height will be assessed in duplicate with a wall-mounted stadiometer at baseline.

Quality of life. General health-related quality of life (HRQOL) will be assessed by the Short Form (SF)-36, which contains 36 items that measure subjective health status.¹¹⁹ The scale forms two summary measures—a physical and mental component summary. Scores are transformed using a 0 to 100 scale, with higher scores indicating better HRQOL. Weight-related quality of life will be measured with the 31-item IWQOL-Lite scale.¹²⁰ The measure generates a total score ranging from 0 (worst) to 100 (best).

Diet. Participants will complete two 24-hour dietary recalls at each assessment point. During each assessment, one 24-hour recall will be conducted during an in-person study visit, and one will be conducted over the telephone within 7 days of the primary assessment. We will use the version of the assessment that includes questions about portion sizes. The assessments will be

performed by a trained assessor interactively using the Nutrition Data System program (University of Minnesota).¹³⁵ A standard 5-step, multiple-pass method will be used to improve accuracy. Diet information will be summarized into calorie intake and macronutrient composition.

Skin carotenoid levels. Skin carotenoid levels will be measured with the Veggie Meter® (Longevity Link Corporation, Salt Lake City, Utah). The Veggie Meter® is a noninvasive research-grade instrument that detects and quantifies the optical density of skin carotenoids using reflection spectroscopy.¹³⁶ The measure has been validated against plasma carotenoid levels¹³⁷ and is reflective of intake from the past 8 weeks.¹³⁸ The measure is unaffected by an individual's skin melanin concentration.¹³⁹ We will follow the standardized protocol for assessments including using the fingertip three times sequentially and averaging the three scores.¹³⁹⁻¹⁴¹ The same fingertip will be used at all assessment points with preference for the non-dominant ring finger. Scores range from 0 to 800 with higher scores indicating higher skin carotenoid stores. Participants will be told that this is measuring general health and will not be told the specific biomarker being assessed as this may influence intake of these foods.

Cardiometabolic risk factors will be assessed using blood pressure, waist circumference, and pulse. Blood pressure and pulse will be measured on each occasion using an automated monitor. Two readings will be taken on each occasion (at 1-minute intervals), after participants have been seated for at least 5 minutes. Waist circumference (measured horizontally halfway between the lowest rib and the top of the hipbone) to the nearest 0.1 cm will be assessed. Two waist measurements will be obtained at each assessment visit.

Exploratory endpoints. In addition, we will collect exploratory data on mediators and surrogate endpoints. Food insecurity status will be assessed with the 10-item US Adult Food Security Survey Module.¹⁰⁹ At follow-up assessments, we will ask about food insecurity over the past 30 days. Depressive symptoms will be assessed with the Patient Health Questionnaire-8 (PHQ-8),¹⁴² a clinically validated measure (that does not include the suicidality question contained in the PHQ-9). Weight control behaviors will be assessed with the Eating Behavior Inventory (EBI).¹²¹ The EBI is a 26-item measure of behaviors conducive to weight control (e.g., "I carefully watch the quantity of food that I eat.") Scores range from 26 to 130. Higher EBI scores indicate a greater use of weight control behaviors. Psychometric measures of eating behavior will include the Eating Disorder Examination Questionnaire (EDE-Q). The EDE-Q evaluates binge eating episode frequency as well as associated features of disordered eating. Dietary self-efficacy will be measured using the Self-Efficacy for Diet Scale.¹⁴³ Satisfaction with the interventions will be assessed using Likert scales and open-ended questions.

9.2 Safety and Other Assessments

Safety evaluations include adverse events (AEs) and assessment of blood pressure and heart rate. In the event of adverse mental health events, participants will be referred to a psychologist or psychiatrist for further evaluation, if required. For all non-study-related medical events, participants will be referred to their own primary care provider.

